8.5. Subgroup Analyses

Subgroup analyses may be performed on selected outcomes in subgroups of interest. All subgroup analyses will be exploratory in nature. As the interest will be on how different treatment regimens work in a specific subgroup, instead of whether the treatment differences are the same across different subgroups, the subgroup analyses will be performed by analyzing the outcome data in different subgroups, instead of analyzing the outcome data in the whole population with subgroup factors included in the analyses model.

Subgroup analyses will be performed for the primary endpoint and the secondary endpoints to determine whether significant differences exist in primary and secondary endpoint results between subgroups.

These subgroup analyses will be carried out using the subjects from the randomized population.

The list of potential subgroups (with applicable definitions in parentheses) includes, but is not necessarily limited to, the following:

- baseline HbA1c (<8.4% and \geq 8.4%)
- baseline morning PPG (<13.5 mmol/L and \geq 13.5 mmol/L)
- baseline morning BG excursion (<4.4 mmol/L and \geq 4.4 mmol/L)
- baseline body mass index (BMI) (<25 and \geq 25)
- gender (male and female)
- 3-month persistence (discontinued insulin in the first 3 months of treatment or not)

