Secondary Analyses: For change from baseline in venous fasting plasma glucose (FPG), finger stick blood glucose (FSBG)-based fasting blood glucose (FBG), post prandial glucose (PPG) and blood glucose (BG) excursion, the analyses model will be similar to the primary analyses model, except that the comparison will be based on the treatment contrast p-value from the ANCOVA model.

For percentages of patients reaching treatment goals (<7%) at Week 24 and Week 48, no missing data will be imputed. Count and percentages of patients reaching treatment goals will be summarized, and also be analyzed by a logistic regression model, with logit link function, treatment as fixed effect and baseline HbA1c as continuous covariate.

Insulin dose at each visit will be descriptively summarized by treatment groups by total daily dose (IU and IU/kg).

Safety: The incidence rate of case report form (CRF) collected severe, nocturnal and total hypoglycemic events will be summarized by visit and for the overall study duration. Pairwise comparison between treatment arms will be performed by Fisher's exact test. The overall yearly rates (events/patient/year) of those hypoglycemic events, calculated as, for each patient, the number of episodes times 365.25 and then divided by the patient's treatment duration, will be summarized, and analyzed by a negative-binomial regression model with treatment as fixed effects and log of (patient's treatment duration/365.25) as an offset variable.

Other Analyses: For the medial resource utilization and patient-reported outcome measurements summary statistics will be provided and comparison will be performed by appropriate general test.

Subgroup analysis will be performed for baseline HbA1c, baseline morning PPG, BG excursion, gender, and persistence levels in 2 treatment groups.

2. Schedule of Activities

Table IOQR.1. Schedule of Activities for Prospective Cohorts

eCRF Visit No.:	1	2	3	4	5	6	ET ^a
Week of treatment	0	4	12	24	36	48	ET
Visit Window (days)	–	±7	±7	±7	±14	±14	±14
Informed consent (before procedures/tests)	X						
Demographics	X						
Weight	X	X	X	X	X	X	X
Height	X						
Local urine pregnancy test ^b	X						
Duration of diabetes	X						
Anti-hyperglycemic medications(Non-insulin)	X	X	X	X	X	X	X
Insulin treatment ^c	X	X	X	X	X	X	X
Insulin dose ^d	X	X	X	X	X	X	X
Preexisting conditions/Adverse events ^e	X	X	X	X	X	X	X
Severe, nocturnal and total hypoglycemia events ^f	X	X	X	X	X	X	X

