10.3.6.2. Subgroup Analyses

Subgroup analyses may be performed on selected outcomes in subgroups of interest. All subgroup analyses will be exploratory in nature. As the interest will be on how different treatment regimens work in a specific subgroup, instead of whether the treatment differences are the same across different subgroups, the subgroup analyses will be performed by analyzing the outcome data in different subgroups, instead of analyzing the outcome data in the whole population with subgroup factors included in the analyses model.

The following subgroups will be explored, and additional subgroups may be further explored if needed:

- baseline HbA1c (<8.4% and \geq 8.4%)
- baseline morning PPG (<13.5 mmol/L and \geq 13.5 mmol/L)
- baseline morning BG excursion (<4.4 mmol/L and \geq 4.4 mmol/L)
- baseline body mass index (BMI) (<25 and \geq 25)
- gender (male and female)
- 3-month persistence (discontinued insulin in the first 3 months of treatment or not)

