9. To compare time to insulin treatment change between insulin analog mid mixture BID and basal insulin analog QD treatments	
9. Time to insulin treatment change: Defined as time to any of: insulin treatment discontinuation, switch, intensification or reduction in frequency
 
Discontinuation: Defined as stopping insulin treatment for 30 days or more.
 
Switch: Defined as stop the initial insulin therapy and started another insulin therapy of different class.
 
Intensification: Defined as any of the following: adding meal time insulin in basal insulin analog QD group; changing from BID to TID in insulin analog mid mixture BID group
 
Reduction in frequency: Defined as any of the following: changing from BID to QD; changing from TID to BID or QD

10. To compare the proportion of patients who achieve the HbA1c <7% without switching and discontinuing study insulin, and without using rescue therapy between insulin analog mid mixture BID and basal insulin analog QD treatments	10. Proportion of patients who achieve the HbA1c <7% without switching and discontinuing study insulin, and without using rescue therapy
11. To compare the patients-reported self-efficacy related to insulin therapy as assessed using SEITQ between insulin analog mid mixture BID and basal insulin analog QD treatments	11. The change in SEITQ score form baseline at 48 weeks

Tertiary/Exploratory	

12. To compare the insulin treatment pattern for
 
 • discontinuation • switch • intensification • reduction in frequency 
between insulin analog mid mixture BID and basal insulin analog QD treatments
	
12. Time to insulin discontinuation, switch, intensification or reduction in frequency
 
Proportion of patients who experience insulin discontinuation, switch, intensification or reduction in frequency during 48 weeks

13. To compare healthcare resource utilization (all-cause and T2DM-related; inpatient, outpatient and ER) between insulin analog mid mixture BID and basal insulin analog QD treatments
	
13. Healthcare resource utilization (all-cause and T2DM-related; inpatient, outpatient and ER) during 48 weeks

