5. SAMPLE SIZE DETERMINATION

The primary objective of the study will be evaluated using the classification method as proposed by Qu and colleagues (2011). With no prior hypothesis specified, the study will be considered a success if a conclusion may be reached by the classification method. With a 1:1 randomization ratio between insulin analog mid mixture BID and basal insulin analog QD, and assuming a non-inferiority margin of 0.4%, no treatment difference between mid mixture BID and basal insulin analog QD, and a common SD of 1.5% for the change from baseline in HbA1c at Week 24, 332 evaluable patients per arm will provide greater than 99% possibility for the study to reach a conclusion for primary analyses with 2-sided alpha level of 0.05. If we assume 20% of the patients will drop out without providing an evaluable post-baseline HbA1c, 415 patients per arm need to be randomized.

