Discontinuation: Defined as stopping insulin treatment for 30 days or more.

Switch: Defined as stop the initial insulin therapy and started another insulin therapy of different class.

Intensification: Defined as any of the following: adding meal time insulin in basal insulin analog QD group; changing from BID to TID in insulin analog mid mixture BID group

Reduction in frequency: Defined as any of the following: changing from BID to QD; changing from TID to BID or QD.

Plots of time to event by weeks will be used to display the results of endpoints.

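### SAP 8.5 states a between-subgroup aim that its own first paragraph and Protocol 10.3.6.2 disclaim, and both documents list 3-month persistence, known only after randomisation, as a subgroup for comparing arms

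*SAP*

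**What the plan says.** **Aim and method.** The first paragraph of SAP 8.5 repeats Protocol 10.3.6.2. Subgroup analyses may be done on selected outcomes and are exploratory. The interest is in how the regimens work within a subgroup, "instead of whether the treatment differences are the same across different subgroups". Each subgroup is analysed separately, "instead of analyzing the outcome data in the whole population with subgroup factors included in the analyses model".

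The second paragraph of SAP 8.5 has no counterpart in the protocol. It says the analyses will be done for the primary and the secondary endpoints "to determine whether significant differences exist in primary and secondary endpoint results between subgroups".

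**Subgroups.** SAP 8.5 and Protocol 10.3.6.2 give the same six factors. Five are fixed at baseline: HbA1c, morning PPG, morning BG excursion, BMI and gender. The sixth is "3-month persistence (discontinued insulin in the first 3 months of treatment or not"). The synopsis (Protocol Section 1, Other Analyses) abbreviates this to "gender, and persistence levels in 2 treatment groups".

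**Discontinuation as an outcome.** SAP 8.2.2 item 6 has "Discontinuation: Defined as stopping insulin treatment for 30 days or more" as one component of time to insulin treatment change (endpoint 9). Endpoint 10 counts success only in patients who have not discontinued. Endpoint 12 includes "Proportion of patients who experience insulin discontinuation, switch, intensification or reduction in frequency during 48 weeks".

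**The concern.** The two paragraphs of SAP 8.5 cannot both be followed. They differ on aim (within subgroups or between them) and on scope (selected outcomes, possibly, or all primary and secondary endpoints, definitely). The only output planned is a set of separate within-subgroup results. An analyst asked to meet the second aim from those results will be drawn to note that one subgroup is significant and the other is not. That is not a test of a difference, and the pattern is common when the effect is uniform.

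Persistence is a different problem, and the two documents share it. Whether a patient stops insulin in the first 3 months is known only after randomisation and can depend on the arm. Persisters in one arm need not resemble persisters in the other, and the same holds for discontinuers. A difference between arms within either group may reflect who stopped rather than what the regimen did.

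**Working it through.** **Inputs from the documents (SAP 5, Protocol 10.1):** 332 evaluable per arm, margin 0.4, 20% dropout, two-sided 5%, and "a common SD of 1.5% for the change from baseline in HbA1c at Week 24".

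**The plan's own figure.** SE = 1.5 × √(2/332) = 0.116, and the 95% CI half-width is 1.96 × 0.116 = 0.228. This is below 0.4, so L > -0.4 or U < 0.4 must hold, which agrees with the stated probability above 99%. Also 332/0.80 = 415. The design figures reproduce and are not in question.

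**Part 1: same effect, two halves.** Assumed: a 50:50 split (166 per arm in each half) and residual SD 1.5 within each half. Significant means that the 95% CI excludes 0.

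- SE per half = 1.5 × √(2/166) = 0.1646.
- p = Φ(d/SE - 1.96) + Φ(-d/SE - 1.96), where d is the true difference.
- P(exactly one half significant) = 2p(1 - p).

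| True difference d | p per half | Exactly one significant |
|---|---|---|
| 0 | 0.050 | 9.5% |
| 0.2 | 0.229 | 35% |
| 0.4 | 0.681 | 43% |

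If the residual SD were 1.2 (SE 0.1317), the last column would read 9.5%, 44% and 24%.

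A direct contrast of the two halves has SE = √(0.1646² + 0.1646²) = 0.233. Its power for a 0.4-point between-subgroup difference is Φ(0.4/0.233 - 1.96), about 40%. The difference detectable with 80% power is about 0.65.

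**Part 2: persistence, with no true treatment effect.** The documents give no discontinuation rates and no correlation with response, so everything here except SD 1.5 is assumed. A latent tendency to stop has correlation ρ with poor HbA1c response. Fractions a and b stop in the two arms (a < b), z is the corresponding normal quantile and φ the normal density. A positive value favours the arm with more discontinuation.

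- Persisters: 1.5 × [ρ_b φ(z_b)/(1 - b) - ρ_a φ(z_a)/(1 - a)]
- Discontinuers: 1.5 × [ρ_a φ(z_a)/a - ρ_b φ(z_b)/b]

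For 10% v 20%, φ(z) = 0.1755 and 0.2800. The persister ratios are then 0.195 and 0.350, and the discontinuer ratios 1.755 and 1.400.

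| ρ in 10% arm | ρ in 20% arm | Persisters | Discontinuers |
|---|---|---|---|
| 0.3 | 0.3 | 0.07 | 0.16 |
| 0.7 | 0.7 | 0.16 | 0.37 |
| 0.7 | 0.3 | -0.05 | 1.21 |
| 0.3 | 0.7 | 0.28 | -0.68 |

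The bias is zero if ρ = 0 in both arms, or if rates and mechanism match across arms. Precision among discontinuers is also poor. If they are evaluable in proportion, there are about 33 v 66 patients, the SE is 1.5 × √(1/33.2 + 1/66.4) = 0.319, and the 95% CI is about ±0.6 points.

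**Overlap with endpoints.** If the 30-day definition also governs the subgroup, which SAP 8.5 does not state, every patient in the discontinued stratum fails endpoint 10 by construction and has had an early endpoint 9 event. Endpoints 9 and 10 are secondary, so the second paragraph of SAP 8.5 would put both through this subgroup analysis.

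**The case against.** The strongest reply is that nothing important turns on this. Both documents call all subgroup analyses exploratory, the first paragraph of SAP 8.5 fixes the method, and no listed output depends on the stray sentence. The 35% and 43% describe a misreading rather than a planned test. This stands as a limit on importance. It does not reconcile two opposite aims, and an exploratory label does not turn a post-randomisation stratum into a randomised comparison.

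Four stronger readings are tempting, and the documents do not support them.

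- *Separate analyses can never address a between-subgroup difference.* They can. The two levels of a factor are disjoint sets of patients, so two estimates and their SEs give a contrast with a CI. The defect is that neither document specifies one.
- *The arm with more discontinuation will look better in both strata.* This holds when the correlation is the same in both arms. The last two rows of the persistence table reverse it in one stratum or the other.
- *The missing 3-month definition in the synopsis is an inconsistency.* The synopsis gives no cut-off for any subgroup, so this is ordinary abbreviation.
- *Persistence is an SAP departure from the protocol.* Both lists contain it in the same words.

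It is also fair to say that the persistence subgroup and endpoints 9, 10 and 12 overlap without being identical. The endpoints 9 and 12 definition uses a 30-day stop, and endpoint 12 runs over 48 weeks. The subgroup covers 3 months and states no 30-day rule.

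**Conclusion.** Both parts hold and should be corrected.

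(1) SAP 8.5 contradicts itself and Protocol 10.3.6.2 on the aim and scope of the subgroup analyses, and specifies no comparison that would serve the between-subgroup aim. Reading significance across subgroups would mislead in roughly 10% to 43% of trials with a uniform effect of 0 to 0.4 points, assuming equal halves and SD 1.5.

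(2) Arm comparisons within 3-month persistence, listed in both documents, are not randomised comparisons and may be biased. Size and direction are unknown. The 0.07-0.16 and 0.16-0.37 points for 10% v 20% discontinuing rest on assumed rates and an equal correlation of 0.3-0.7 in both arms. They can be larger, reversed or zero under other mechanisms.

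A reader might infer that the primary result is at risk. It is not: the primary analysis uses all randomised patients with Week 24 data and does not depend on any subgroup.

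**What to change.** **Part 1.** Delete the whole second-paragraph sentence of SAP 8.5, and make no between-subgroup claims. Removing only the clause on differences between subgroups would leave the commitment to all primary and secondary endpoints, which still conflicts with the optional, selected-outcomes wording in the first paragraph and in Protocol 10.3.6.2. The cost is one SAP sentence.

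Only if the sponsor wants the between-subgroup aim, amend both documents. Report the between-subgroup difference in treatment effect with its 95% CI for the five baseline factors, either from an interaction term or from the two separate estimates with SE = √(SE1² + SE2²). Label it exploratory and unadjusted for multiplicity, and state its low power (about 40% for 0.4 points at a 50:50 split and SD 1.5). This reverses an explicit protocol choice, so it costs a protocol edit as well.

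**Part 2.** Remove 3-month persistence from the arm-comparison subgroups in Protocol 10.3.6.2, SAP 8.5 and the synopsis list. Report outcomes by persistence status descriptively within each arm, labelled non-randomised, with no between-arm test. The cost is a small edit to both documents, and the arm comparison by persistence status is no longer tested. Data collection, sample size and the primary analysis do not change.

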8.6. Interim Analyses

An interim analysis may be conducted after all patients complete Visit 4. The analysis will include the primary objective and key secondary objectives. Although the study is open label, in order to avoid influencing study conduct in any way, should the interim analyses be performed, results will not be publicly disclosed until the last patient completes Visit 6.

